#### 5. Background and Rationale: (Describe the research question and justification for undertaking the study explaining the aspects of novelty in the study)

Polycystic ovary syndrome (PCOS) is one of the most common endocrinopathies, affecting approximately 9% to 18% of women in reproductive age. Although the exact pathogenesis of PCOS remains unclear, the characteristic symptoms include oligoanovulation, polycystic ovarian morphology could be explained by hyperandrogenism and hyperestrogenemic not balanced by progesterone. The endocrine, inflammatory, and metabolic changes associated with PCOS have consequences for vision, including neurovascular, metabolic changes in the retina, macular and optic nerve thickness changes.

In recent years it has been discovered that female sex steroids have both systemic and ocular effects, Estrogen, progesterone and androgen receptors have been found in the cornea, lens, iris, ciliary body, retina, lacrimal glands, meibomian glands and conjunctiva, The influence of hormone replacement therapy in menopausal women remains unclear, as some authors support the idea that it improves the quality and the volume of the tear film, whereas others have shown that it increases the risk of dry eye, It's possible that HRT may alleviate postmenopausal dry-eye symptoms by increasing goblet cell density. However, other studies suggest that HRT worsens dry-eye symptoms in some cases, and estrogen-only HRT seems to be worse than a combined estrogen and progesterone therapy.

Reports are stressing on the effect of PCOS on tear film stability rather than amount of the tears denoting the possible effect on meibomian glands (MGs) functions, Loss and morphological deterioration of the MGs are observed in PCOS patients, Yonca Asfuroglu et al. reported that Dry eye was well established in patients with PCOS. They proposed that hyperandrogenism, insulin resistance and subclinical inflammation may be possible contributing factors to the Dry eye spectrum in these patients, They correlated the severity of the Dry eye with the level of inflammation and hyperandrogenism.

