**8. Study Methods**

- **Population of study:** (Please provide all details regarding participants including gender, age range and disease conditions. Also indicate if this protocol involves children, prisoners, pregnant women or cognitively impaired or mentally disabled subjects)

Two groups with confirmed laboratory and ultrasonography diagnosis of PCOS , First group will include 30 eyes of 30 females in childbearing period (18-40 years old) scheduled for treatment for non- fertility indications with oral contraceptive pills (as a first line of treatment), and the second group will include 30 eyes of 30 females in childbearing period (18-40 years old) scheduled for treatment with Clomiphene citrate (as a first line of treatment), for fertility indications.

- **Study location:** (Please provide where the study will be conducted and from where study participants will be recruited)

Patients will be recruited from gynecology and dermatology Kasr Al-Ainy clinics and will undergo their ophthalmic examination and investigations at the department of ophthalmology, Kasr Al-Ainy school of medicine.

- **Inclusion criteria:**

1. Females at child bearing period (18-40 years old).
2. Patients recently diagnosed with polycystic ovarian syndrome.

- **Exclusion criteria:**

1. Patients who were diagnosed with Dry eye disease.
2. Patients who were treated with hormonal replacement therapy, Metformin, Aromatase inhibitors, clomiphene citrate or androgen antagonists.
3. Patients who underwent ocular surgeries.
4. Patients with history of diabetes mellitus or hypertension.

- **Methodology in details:**

Two groups with confirmed laboratory and ultrasonography diagnosis of PCOS, First group will include 30 eyes of 30 females in childbearing period (18-40 years old) scheduled for treatment for non- fertility indications with Estradiol valerate / Norgestre tablets for six months, The second group will include 30 eyes of 30 females in childbearing period (18-40 years old) scheduled for treatment with Clomiphene citrate for fertility indications for 6 months.

- Follicle stimulating hormone (FSH), luteinizing hormone (LH) , androgen, estrogen, progesterone , fasting insulin and neutrophil to lymphocyte ratio (NLR) will be obtained.
- The two groups will undergo complete ophthalmic examination including :

\*Full history.

\*Standard Patient Evaluation of Eye Dryness Questionnaire (SPEED) in order to quickly track the progression of dry eye symptoms over time.

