\*Manifest refraction.

\* Corrected distance visual acuity.

\* Anterior segment examination using slit lamp, Schirmer's test and tear film breakup time test.

\* Fundus examination.

\* Measuring central corneal thickness (CCT) using Corneal pachymetry.

•Beside Schirmer's test, tear film breakup time test and fluorescein break-up patterns, Dry eye assessment will be performed using Dry Eye Diagnostic System device (D130, Medi-Works Precision Instruments; Shanghai, China). Device to have a Dry eye diagnosis brings out an automatic result of non-invasive break up test (NIBUT) and tear meniscus height after taking one video. It is a fully automatic analysis system to provide efficient quantified evaluation for the overall stability of the tear film. Also it uses identification system that depicts the tear meniscus area and measures the tear height automatically.

The device also automatically analyses the meibomian glands, lipid layer thickness, and eyelid margin. The built-in infrared lighting system helps to obtain the enormous image scope of the meibomian glands. Finally the device identifies and calculates percentages of

conjunctival congestion and ciliary congestion, Thus evaluating the severity of eye congestion. If the degree of severity of eye congestion is more than two, it is abnormal.  
\*Examination and laboratory tests will be done before, 3 months after starting treatment and after finishing the treatment course.

- **Intervention:**

☒ Diagnostic intervention (please describe):

Imaging ocular surface using dry eye diagnostic system.

☐ Therapeutic intervention (please describe):

☐ No intervention

- **Does the research involve?**

☒ Human participants

☐ Biological samples/Tissues

☐ Identifiable private data/Information

- **Type of consent of study participants:**

☒ Written consent

[figure not shown]
☐ Oral consent

☐ No consent needed (Please justify)

- **Potential risks:**

(Please mention all risks involved even mild ones as pain, discomfort, chance of infection or psychological effects)

1- No possible risks

- **Confidentiality of data:** (Please explain how privacy and confidentiality of data and records will be maintained)
- Names and private data of patients will not be published, only the results of the study will be analyzed and published.

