### 9- Study outcomes:

- **Primary outcomes** (Most important measurable outcomes)
  - 1- Measuring changes in meibomian glands function, break up time, tear meniscus height, and lipid layer thickness in polycystic ovarian syndrome and with different drugs used in managing it.
- **Secondary outcome parameters** (other outcomes to be assessed)
  - 1- Measuring eye lid margin, conjunctival hyperemia, and ocular surface staining in polycystic ovarian syndrome and with different drugs used in managing it.
  - 2- Measuring the central corneal thickness (CCT) changes in polycystic ovarian syndrome and with different drugs used in managing it.

**10- Sample size** (number of study subjects included and justification including the clinical and statistical assumptions supporting sample size calculation)

$$\left( \frac{Z_{a/2} + Z_B}{P_1 - P_2} \right)^2 (p_1 q_1 + p_2 q_2)$$

(Takazawa & Morita, 2020)

n = sample size

Z a/2 (The critical value that divides the central 95% of the Z distribution)

ZB (The critical value that divides the central 20% of the Z distribution)

p1 = prevalence in case group

p2 = prevalence in control group.

q = 1-p

Epi Info STATCALC was used to calculate the sample size by considering the following assumptions:- 95% two-sided confidence level, with a power of 80%. &  $\alpha$  error of 10% . The final maximum sample size taken from the Epi- Info output was 26. Thus, the sample size was increased to 30 subjects with total 30 eyes in each group to assume any drop out cases during follow up.

[figure not shown]
**11- Statistical analysis** (Please describe your data analysis plan)

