Data management and analysis will performed using Statistical Package for Social Sciences (SPSS). Median and range for non-parametric measures and ordinal (scores) data. Numerical data will be presented as means  $\pm$  standard deviations (SD). Categorical data will be presented as number and percentages %. Pairwise comparisons between the two groups for normally distributed variables will be done using the Student's t-test; the Mann-Whitney test, a nonparametric test equivalent to the t-test, will be used in non-normally distributed variables. The Repeated measures ANOVA test will be used to compare the effect change within and between the study groups at different visits. The chi-square test or the Fisher's exact test will be used to compare between the groups with respect to categorical data. All p-values will be two-sided. P-values  $< 0.05$  will be considered significant

**12- Source of funding:** (Please include source of funding even if self funding)

- Faculty of Medicine, Cairo University ☐
  - Other sources: ☐
- Please specify: Self-funding

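### The last visit has no date counted from treatment start, and the plan has no rule for pregnancy although one group takes clomiphene for fertility; data from women who conceive may be early, taken in pregnancy, or missing.

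*Combined protocol and SAP*

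**What the plan says.** Section 8 (Study Methods) defines two non-randomised groups of 30 women. One is "scheduled for treatment with Clomiphene citrate for fertility indications for 6 months". The other is treated for "non- fertility indications with Estradiol valerate / Norgestre tablets for six months". Visits are set in one sentence: "Examination and laboratory tests will be done before, 3 months after starting treatment and after finishing the treatment course". The last visit has neither a month nor a window.

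The template prompt for the study population asks whether pregnant women are involved, and the answer does not say. Pregnancy is also absent from the exclusion criteria, visit schedule, outcomes and analysis. The laboratory list (FSH, LH, then "androgen, estrogen, progesterone , fasting insulin and neutrophil to lymphocyte ratio (NLR) will be obtained") contains no pregnancy test.

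Section 10 takes 26 per group from the sample size software, and then "the sample size was increased to 30 subjects with total 30 eyes in each group" to cover drop-out. Section 11 states: "The Repeated measures ANOVA test will be used to compare the effect change within and between the study groups at different visits". It has no rule for missing visits. Section 5 gives the premise that "female sex steroids have both systemic and ocular effects".

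**The concern.** Conception is the purpose of treatment in one group and is prevented by treatment in the other. It is therefore a foreseeable event that falls almost entirely on one side. For a woman who conceives, the plan does not say whether her course counts as finished, when she is examined, or whether her data are used.

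Either default causes trouble. If she is kept, a measurement taken in pregnancy is counted as an effect of clomiphene, although the study's own rationale is that sex steroids act on the eye. If she is dropped, the clomiphene group shrinks to women who did not conceive, a subset selected by response to treatment. In its standard form repeated measures ANOVA discards every woman with a missing visit, so her usable earlier data would go too. The primary outcomes (meibomian gland function, break-up time, tear meniscus height, lipid layer thickness) are all exposed. So is month 3, because conception can precede it.

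**Working it through.** **Inputs from the documents.** 26 calculated and 30 enrolled per group, and 80% power (section 10); two-sided 0.05 (section 11). Section 10 also mentions a 10% alpha error. That needs reconciling separately, and nothing here depends on it.

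**Assumptions, not in the documents.** Six-month conception probability c from 10% to 50%; conception ends the course and alters sex hormones; the correlation and slope used in step 4.

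**1. The plan's figures.** The 26 cannot be reproduced, because the formula's two prevalences have no values. The step to 30 can: 26/(1 − 4/30) = 30, a margin of 4/30 = 13.3% in each group.

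**2. Is the margin enough?** Non-pregnant women = 30(1 − c). The margin is exceeded when 5 or more of 30 conceive, with X ~ Binomial(30, c) and no other drop-out counted.

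**3. Power.** Section 10 is built on proportions, so I back-solved the standardised difference that 26 v 26 detects with 80% power (noncentral t, two-sided 0.05): 0.79 SD. The last column gives power at that difference with all 30 pill users present.

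| c | Non-pregnant of 30 | P(5 or more conceive) | Power v 30 |
|---|---|---|---|
| 10% | 27 | 0.18 | 0.84 |
| 20% | 24 | 0.75 | 0.81 |
| 30% | 21 | 0.97 | 0.78 |
| 40% | 18 | 0.998 | 0.74 |
| 50% | 15 | 1.00 | 0.69 |

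If the pill group also falls to 26, the 50% row becomes 26 v 15 and power is 0.66. That is the worst case in the range.

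**4. Bias if conceivers are dropped.** Let x be the 3-month change in SD units, with logit P(conceive) = a + x and a set to give overall loss p. The mean of x among non-conceivers, by numerical integration, is −m with m = 0.117, 0.254 and 0.374 at p = 13%, 30% and 45%. The bias in the final change is m times the slope of final change on x.

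- Equal correlation of 0.6 between visits: the SD of a change is √(2 × 0.4) = 0.894 outcome SD and the two changes correlate 0.5, so the slope is 0.447. Bias is 0.05, 0.11 and 0.17 SD.
- Correlation of 0.6 between the two changes themselves: slope 0.6. Bias is 0.07, 0.15 and 0.22 SD of change.

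**5. What a mixed model recovers.** If every woman supplies a month-3 value and loss depends only on observed data, the bias is about zero. If half the conceivers lack month 3, the mean of x among women who have it is −0.5(1 − p)m/(1 − p/2). Multiplied by 0.6, this leaves a bias of 0.03, 0.06 and 0.08 SD.

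**6. Bias if conceivers are kept.** If pregnancy shifts an outcome by δ SD, and all c are pregnant at the last visit, the clomiphene mean shifts by cδ; for example, 0.3δ at c = 30%. The documents give no value for δ.

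**The case against.** A reader might infer that the final data of the whole clomiphene group are compromised. The documents do not support that: the problem concerns only women who conceive, and ordinary drop-out can occur in both groups. Both courses are planned for six months, so the last visit has an implied time of about month 6. What is missing is whether it stays there when a course ends early. That conception ends the course and changes the hormones is plausible but is not written.

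Power is the weaker part of the case. At 10% to 20% conception, power at the back-solved effect stays above 80%, and that effect is not a protocol figure. The size of the bias depends on a model that I chose.

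It can also be said that this is an observational cohort whose groups differ by indication from the start, so the contrast is confounded anyway. That is true, and it lowers the severity. But a cohort comparing changes under two drugs still needs a defined assessment time and a rule for an event that one drug is given to produce. History, estrogen and progesterone are collected and might reveal some pregnancies, but nothing says how such a finding would be used.

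That the last visit follows the end of treatment applies equally to both groups, so it is no evidence of one-sided bias.

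**Conclusion.** The gap is real and should be fixed. The plan does not say when women who conceive have their last assessment or how their data enter the analysis, and the named analysis would in its standard form remove them if a visit is missing. The main harm is a poorly defined comparison with selective loss: roughly 0.05 to 0.2 SD of completer bias over 13% to 45% loss, if conception is related to the 3-month change. The loss of power is moderate: 0.84 down to 0.69 over 10% to 50% conception, against 0.80 planned. The drop-out margin is likely to be exceeded at 20% conception and almost certain to be at 30%.

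Two stronger conclusions are not supported. The final comparison is not void, since non-conceivers still supply valid data and month 3 remains largely usable. Nor does a mixed model remove all bias, because conception before month 3 leaves some women without a usable interim value.

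**What to change.** Before enrolment, amend sections 8 and 11 as follows.

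- Date the last ocular assessment at month 6 from treatment start, within a stated window, whether or not the course has ended.
- At each visit record drug status, pregnancy status and, where relevant, the date of pregnancy, from history or the gynaecology record.
- Replace complete-case repeated measures ANOVA with a mixed model that keeps every earlier visit.
- State in advance how post-conception measurements enter the primary analysis. Setting them aside, with a sensitivity analysis of all measurements, is one defensible choice. Describing women as managed, with pregnancy reported, is another.
- Report conceptions by group.

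The cost is some wording and a few data fields. If post-conception measurements are set aside, month-6 numbers in the clomiphene group will be openly smaller, and some bias remains where conception precedes month 3. Keeping 26 non-pregnant women would need 26/(1 − c) enrolled: 33, 38 or 52 at 20%, 30% or 50% conception. The sponsor may instead accept and report the lower precision. No change to treatment is proposed.

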### 9- Study outcomes:

- **Primary outcomes** (Most important measurable outcomes)
  - 1- Measuring changes in meibomian glands function, break up time, tear meniscus height, and lipid layer thickness in polycystic ovarian syndrome and with different drugs used in managing it.
- **Secondary outcome parameters** (other outcomes to be assessed)
  - 1- Measuring eye lid margin, conjunctival hyperemia, and ocular surface staining in polycystic ovarian syndrome and with different drugs used in managing it.
  - 2- Measuring the central corneal thickness (CCT) changes in polycystic ovarian syndrome and with different drugs used in managing it.

**10- Sample size** (number of study subjects included and justification including the clinical and statistical assumptions supporting sample size calculation)

$$\left( \frac{Z_{a/2} + Z_B}{P_1 - P_2} \right)^2 (p_1 q_1 + p_2 q_2)$$

(Takazawa & Morita, 2020)

n = sample size

Z a/2 (The critical value that divides the central 95% of the Z distribution)

ZB (The critical value that divides the central 20% of the Z distribution)

p1 = prevalence in case group

p2 = prevalence in control group.

q = 1-p

Epi Info STATCALC was used to calculate the sample size by considering the following assumptions:- 95% two-sided confidence level, with a power of 80%. &  $\alpha$  error of 10% . The final maximum sample size taken from the Epi- Info output was 26. Thus, the sample size was increased to 30 subjects with total 30 eyes in each group to assume any drop out cases during follow up.

[figure not shown]
**11- Statistical analysis** (Please describe your data analysis plan)

Data management and analysis will performed using Statistical Package for Social Sciences (SPSS). Median and range for non-parametric measures and ordinal (scores) data. Numerical data will be presented as means  $\pm$  standard deviations (SD). Categorical data will be presented as number and percentages %. Pairwise comparisons between the two groups for normally distributed variables will be done using the Student's t-test; the Mann-Whitney test, a nonparametric test equivalent to the t-test, will be used in non-normally distributed variables. The Repeated measures ANOVA test will be used to compare the effect change within and between the study groups at different visits. The chi-square test or the Fisher's exact test will be used to compare between the groups with respect to categorical data. All p-values will be two-sided. P-values  $< 0.05$  will be considered significant

**12- Source of funding:** (Please include source of funding even if self funding)

- Faculty of Medicine, Cairo University ☐
  - Other sources: ☐
- Please specify: Self-funding

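### Four co-equal primary outcomes, all judged at P < 0.05 with no deciding outcome, visit or test, give a 14–19% chance of a false primary finding even with one test each

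*Combined protocol and SAP*

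**What the plan says.** Section 9 has a single primary item: "Measuring changes in meibomian glands function, break up time, tear meniscus height, and lipid layer thickness", in polycystic ovarian syndrome and under the drugs used to manage it. It does not rank the four measurements, combine them, or say at which visit they decide the question.

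Section 8 sets three assessments: "Examination and laboratory tests will be done before, 3 months after starting treatment and after finishing the treatment course". The course is six months in both groups. Break-up time is obtained in more than one way. There is a "tear film breakup time test and fluorescein break-up patterns", and the dry eye device separately gives an automatic non-invasive break-up time (NIBUT). For the glands, section 8 says "The device also automatically analyses the meibomian glands, lipid layer thickness, and eyelid margin" and describes infrared imaging, but it names no score or functional measure.

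Section 11 plans a t-test or Mann-Whitney test between the groups, without saying at which visits. It also plans a repeated measures ANOVA within and between groups across visits, without saying which effect decides. On the threshold it says "All p-values will be two-sided", and any value below 0.05 "will be considered significant". It contains no multiplicity adjustment and no rule for when the primary objective is met.

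**The concern.** With four equal primary outcomes and a 0.05 threshold on each, a reader will take any one significant result as a positive primary finding. The 5% threshold then applies to each test, while the error rate for the primary objective as a whole is higher. The plan also leaves open which visit, test and break-up time method count, and what stands for gland function. Each of these choices could be made after the data are seen. What is at stake is whether a reported effect of either drug on the ocular surface can be told apart from the best of several chance results in 30 women per group.

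**Working it through.** The documents state no family-wise error rate, so there is no plan figure to reproduce. The only computed figure is the sample size of 26 in section 10. It cannot be checked, because the two prevalences in its formula are not given.

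**Inputs from the documents**
- Primary outcomes: 4 (section 9).
- Threshold: 0.05, two-sided, for every test (section 11). Section 10 gives a "95% two-sided confidence level, with a power of 80"%, but puts an α error of 10% beside it. The calculation uses 0.05, the level that section 11 applies to the tests.
- Visits: 3 (section 8).
- Size: 30 per group (section 10).

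**Assumed, because the documents give no values**
- Every null hypothesis is true.
- Correlation between outcomes is 0 to 0.6 in step 1 and 0 to 0.5 in step 2.
- Correlation between visits is 0.3 to 0.7 (step 2 only).

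**Step 1: one test per outcome.** With independent outcomes, the chance of at least one false finding is 1 − (1 − 0.05)^4 = 1 − 0.8145 = 18.5%. For correlated outcomes, simulating four equally correlated normal test statistics gives:

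| Outcome correlation | At least one P < 0.05 |
|---|---|
| 0 | 18.5% |
| 0.3 | 17.4% |
| 0.5 | 15.5% |
| 0.6 | 14.4% |

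This is roughly three to four times the nominal 5%, and it needs no view on how many tests each outcome receives.

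**Step 2: more than one test per outcome.** Section 11 allows several readings. Simulated trials at 30 per group give:

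| Tests counted on the four outcomes | Number | At least one P < 0.05 |
|---|---|---|
| ANOVA group-by-visit term only (one test each, for comparison) | 4 | 16–19% |
| t-tests at the two post-baseline visits | 8 | 25–32% |
| ANOVA group effect and group-by-visit term | 8 | 29–33% |
| Final-visit t-test and both ANOVA effects | 12 | 33–39% |
| Both post-baseline t-tests and both ANOVA effects | 16 | 37–45% |
| t-tests at all three visits and both ANOVA effects | 20 | 40–51% |

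The last row includes baseline comparisons, which cannot be treatment findings. Without it the range is about 25–45%. Within-group tests and the choice between break-up time methods are not counted in any row.

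**Step 3: after a fix.** One named measure, visit and test gives 5%. Four primaries tested at 0.05/4 = 0.0125 give at most 5%. If they are independent, the rate is 1 − (1 − 0.0125)^4 = 4.9%.

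**Step 4: the power cost of keeping four.** The documents give no effect in SD units. An illustrative effect of 0.79 SD is assumed here because it gives 80% power at 26 per group and two-sided 5%. At 30 per group, the power of a t-test for that effect is about 85% at 0.05 and 69% at 0.0125. In terms of detectable effect, the normal approximation (z for α + z for power) × √(2/30) gives (1.960 + 0.842) × 0.258 = 0.72 SD at 0.05, and (2.498 + 0.842) × 0.258 = 0.86 SD at 0.0125, both for 80% power.

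**The case against.** The strongest reply is that section 11 assigns change across visits to the repeated measures ANOVA alone. The primary outcomes are changes, so the group-by-visit term could be the one test per outcome, with the t-test as a general tool for other comparisons. That is a fair reading. It means the plan does not fix a count of a dozen or more tests. A reader might infer a single figure of about 36–46% across the planned between-group tests. The documents do not support that, because it requires choosing the visits for the t-tests, counting both ANOVA effects and assuming correlations. The reply does not remove the problem, since four tests still give 16–19% on that reading.

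A second reply is that section 7 marks a cohort study and no success rule is stated, so nothing is formally claimed. But section 9 labels outcomes as primary and section 11 sets a significance threshold. If the aim is exploratory, the plan should say so and drop significance claims.

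A third reply stands in full. These rates assume all nulls are true. The groups are not randomised and differ by treatment indication, so real differences unrelated to the drugs are plausible. The rates measure multiplicity only and are not the study's overall chance of a wrong conclusion.

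Finally, the unnamed gland measure and the two break-up time methods are problems of outcome definition. They widen the scope for choice but do not enter the figures.

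**Conclusion.** The concern holds. Followed exactly, sections 9 and 11 give a false-positive chance for the primary objective of 18.5% if the outcomes are independent, and about 14–17% at assumed correlations of 0.6 down to 0.3, with one test per outcome. This is the firm part, since it rests only on the four outcomes, the 0.05 threshold, true nulls and the stated correlations. The range of about 25–50% is conditional on counting more than one test per outcome and on assumed correlations between outcomes and visits. It shows what the open wording permits and should not be reported as the plan's error rate. The 0.79 SD effect is likewise an illustration and not a design value of this study. The plan should be changed before the data are seen.

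**What to change.** In sections 9 and 11, before data are seen, choose one of two routes.

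1. **One primary.** Name one measure, visit and test. An example is the between-group difference in change from baseline to end of treatment in device-measured NIBUT, at two-sided 5%. Test the other three outcomes as key secondary outcomes with Holm. NIBUT is one reasonable choice; another of the four would also do if it is named and justified.
2. **Four primaries.** Give each one test, the between-group difference in change to end of treatment, and apply Holm across the four.

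Under either route, state which break-up time method is used, and replace the reference to meibomian gland function with the gland measure that the device actually reports. Section 8 does not say what that output is, so it has to be established first. Report within-group changes and all other tests with confidence intervals and no significance claim.

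The cost is mainly wording, and fewer results that can be called significant. Within-drug change, which is part of the objective, becomes a matter of estimation. Section 10 is built on two prevalences, so a continuous primary measure would need a matching statement of the effect that 30 per group can detect. The second route also costs power: at 30 per group and the assumed 0.79 SD, it falls from about 85% to 69% at the strictest Holm step of 0.0125.

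### The sample size is justified with a case-versus-control prevalence formula, so the stated 80% power applies to no specified primary comparison of this two-drug cohort

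*Combined protocol and SAP*

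**What the plan says.** Section 10 (Sample size) prints the usual unpooled formula for comparing two independent proportions. It defines the inputs as "p1 = prevalence in case group" and "p2 = prevalence in control group", without naming the condition whose prevalence is meant. The assumptions are a "95% two-sided confidence level, with a power of 80" per cent, and the same sentence adds an alpha error of 10%. The result is reported as "The final maximum sample size taken from the Epi- Info output was 26", and the next sentence raises this to 30 women (30 eyes) in each group to allow for dropout.

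Section 8 (Population of study; Methodology) describes two PCOS groups, one scheduled for an oral contraceptive and one for clomiphene citrate. There is no untreated or non-PCOS group.

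Section 9 gives the primary outcome as "Measuring changes in meibomian glands function, break up time, tear meniscus height, and lipid layer thickness". Section 11 covers between-group comparisons: "Pairwise comparisons between the two groups for normally distributed variables will be done" with Student's t-test, or with Mann-Whitney if the data are not normal. Repeated measures ANOVA is used for change across visits, and chi-square or Fisher's exact test for categorical data in general. It adds that "All p-values will be two-sided" and sets significance at 0.05.

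**The concern.** A sample-size statement should tell the reader what difference the planned primary comparison can detect. This one describes a different study. The formula needs a case group, a control group and a binary condition; the design has two treated patient groups and primary outcomes expressed as changes in measures.

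What is at stake is how the result is read. The study compares drugs. If it finds no significant difference, a reader who trusts the stated 80% power may conclude that the drugs act alike on the ocular surface. The plan gives no basis for that, because it never says how large a difference in change it was powered to find.

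**Working it through.** **1. Inputs.** From section 10: two-sided 95% confidence (alpha 0.05, z = 1.960), a second alpha of 10% (z = 1.645), 80% power and n = 26. Section 10 describes Z_B as the value bounding the central 20% of the normal distribution, which would be 0.253; the value for 80% power is 0.842, used here. The text gives no p1 or p2, and the document gives no SD, target difference or within-woman correlation. I read 26 as per group, because the next sentence raises it to 30 in each group.

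**2. The plan's own figure.** Without p1 and p2, 26 can be neither reproduced nor refuted. The formula can be solved backwards:

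n = (Z_a/2 + Z_B)² × (p1q1 + p2q2) / (p1 − p2)² = 26, with (1.960 + 0.842)² = 7.849 at alpha 5%.

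| p2 | p1 giving n = 26 | gap |
|---|---|---|
| 0.05 | 0.336 | 0.29 |
| 0.10 | 0.417 | 0.32 |
| 0.20 | 0.551 | 0.35 |
| 0.30 | 0.662 | 0.36 |
| 0.50 | 0.840 | 0.34 |

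Check for the second row: 7.849 × (0.417 × 0.583 + 0.10 × 0.90) / 0.317² = 7.849 × 0.3331 / 0.1005 = 26.0.

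The implied gap depends on the variant. For p2 from 0.05 to 0.50:
- printed formula, alpha 5%: about 29 to 36 points
- printed formula, alpha 10%: about 25 to 33 points
- Fleiss formula with continuity correction, alpha 5%: about 36 to 42 points

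Every variant yields a difference in prevalence. None yields power for a change in a measurement.

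**3. What the same numbers support for a difference in mean change.** Take d as the between-group difference in change divided by the SD of the change. The normal approximation is d = (1.960 + 0.842) × √(2/n):
- n = 26: 2.802 × √(2/26) = 0.78
- n = 30: 2.802 × √(2/30) = 0.72

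The noncentral t gives **0.79** and **0.74**.

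For an illustrative d = 0.5 (my assumption, not the plan's), t-test power is 42% with 26 per group and 48% with 30; 80% power would need 64 per group. For change within one group, a paired t-test with 26 women has 80% power for 0.57 SD of the change.

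**4. Four primary measures.** The figures in step 3 are for a single outcome. If alpha were split equally over the four measures (0.05/4 = 0.0125, again my assumption), the t-based detectable difference with 26 per group rises from 0.79 to about 0.96 SD.

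**The case against.** - **A comparison of proportions is planned.** Section 11 lists chi-square or Fisher tests, and meibomian gland function has no defined scale, so it could be graded. This stands in part: one cannot say that the test behind the formula will never be run. But no binary primary outcome, cut-off or condition is defined, and there is no case/control contrast.
- **The prevalences may be given elsewhere.** A figure that is not shown follows the sample-size paragraph and could hold the software output. This stands, so the point must not rest on missing values of p1 and p2. It rests on their printed definitions.
- **The t-test is not the whole planned analysis.** Power for repeated measures ANOVA over three visits depends on a within-woman correlation that is not given. This stands. The 0.79 is in SDs of change; in single-visit SDs it is 0.79 × √(2(1 − r)), assuming equal variances at the two visits, which is about 0.94, 0.79 or 0.50 for assumed correlations r of 0.3, 0.5 or 0.8.
- **Thirty per group may be enough.** A reader might infer that the study is too small. The documents do not support that: they state no difference that matters, and 30 completers per group would suffice for 0.74 SD or more.
- **A null result would still be readable.** A reader might infer that a non-significant finding could not be interpreted at all. That goes too far, because a confidence interval shows which differences remain plausible whatever formula was used in planning.

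**Conclusion.** The point holds. The sample-size justification concerns a prevalence in cases and controls, and neither that outcome nor that contrast is among the specified primary comparisons, so the stated 80% power attaches to none of them. This follows from the printed text alone and needs no assumption.

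The size of the gap does rest on assumptions: 26 evaluable women per group, a two-sided 5% two-sample t-test of change, and one outcome. On that basis the study has 80% power for 0.79 SD of the change, and would miss a true 0.5 SD difference more often than it found it. Section 10 also contradicts itself, and section 11, by pairing 95% confidence with a 10% alpha error.

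**What to change.** Keep 30 women per group. In section 10, replace the prevalence formula and the case/control wording with a two-means statement for one primary outcome, which the investigators should name from those already collected. Break-up time is one example; if it is chosen, say whether the fluorescein or the non-invasive test is meant. Suggested text:

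> With 30 women per group (26 evaluable), a two-sided 5% t-test has 80% power for a between-group difference in change of 0.79 SD.

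Follow it with that difference in the outcome's own units, using a stated and sourced SD of the change, and say whether a difference of that size would matter clinically. Delete the 10% alpha error. If all four measures stay primary with alpha split equally, give 0.96 SD instead.

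Cost: protocol wording and finding one SD; no extra patients, visits or procedures. The drawback is that the stated sensitivity becomes visibly coarser.
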